## 7.2 Event Dates

Medical events are defined as medical history, prior and concomitant medication, non-drug therapy and procedures, and adverse events.

### 7.2.1 Event Days

All types of events have a Start/Onset Day calculated and, if not ‘Ongoing’, have a Stop/Resolution Day calculated equivalent to Study Day as defined in 7.1.

### 7.2.2 Missing Dates and/or Times

Missing and/or incomplete dates/times for events are imputed for calculating Start Day and End Day only. Dates are listed as missing/incomplete [with “-” replacing missing information]

but the Start/End Day/Time are listed between square brackets to denote it is calculated based on missing data (i.e. [-28], [1], [Ongoing]).

Missing and/or incomplete dates/times are imputed in a manner that assumes the worst-case scenario (i.e., Start as close as possible to the First Study Treatment Administration and stopped such that it is assumed to have lasted for the longest possible duration, considering that the Start date/time should not be after the Stop date/time).

Technically, this is done as follows for End Day/Time:

- For a completely missing stop year (regardless of minute, hour, day, or month response) the event is assumed to be ongoing.
- For a missing stop hour (and the event is not 'Ongoing'):
  - it is assumed to have ended on hour 23 (11pm) of that day
- For a missing stop minute (and the event is not 'Ongoing'):
  - it is assumed to have ended 59 minutes past the hour
- For a missing end day (and the event is not 'Ongoing'):
  - it is assumed to have ended on the last day of the month, if the month is given
  - it is assumed to have ended on the 31st of December of that year, if the month is also missing

Technically, this is done as follows for Start Day/Time:

- For a completely missing Start date (day, month, and year regardless of the minute and hour recorded)
  - the Start Day of the event is "[Pre-Treat]" if the end date or partial end date concludes the event stopped before First Study Treatment Administration (i.e. assumed to be prior or pre-treatment as is applicable).
  - in all other instances (i.e. inconclusive end date or Ongoing event) the Start Day of the event is assumed to be the same date and time as First Study Treatment Administration (i.e. assumed to be concomitant or treatment emergent as applicable.)
- For a missing start hour:
  - it is assumed to have started on hour 00 (midnight) of that day.
  - or at the time (hour and minute) of First Study Treatment Administration if the start date (day, month and year) is the same as the First Study Treatment Administration date.
- For a missing start minute:
  - it is assumed to have started on minute 00 of that hour.
  - or at the time (hour and minute) of First Study Treatment Administration if the start date (day, month and year) is the same as the First Study Treatment Administration date.
- For a missing Start day but given month:
  - it is assumed to have started on the first day of the month.
  - or at the date of First Study Treatment Administration if the start month and the year is the same as the First Study Treatment Administration month and year.
- For a missing start month:
  - it is assumed to have started on the first of January of that year.
  - or at the date of First Study Treatment Administration if the start year is the same as the First Study Treatment Administration year.

### 7.3 Study Treatments

'Table 4: Study Treatments' shows the Study Treatments and how they are labelled in all Listing outputs. The study treatment assigned at baseline is used.

**Table 4: Study Treatments**

Study Treatment	Study Treatment Label
Voltaren Gel 1% (diclofenac sodium)	Voltaren Gel 1%
Voltaren Gel 1.16% (diclofenac diethylammonium)	Voltaren Gel 1.16%
Voltaren Gel 2.32% (diclofenac diethylammonium)	Voltaren Gel 2.32%

## 7.4 Analysis Variables

### 7.4.1 Disposition

Subject disposition data are collected on the 'Study Termination' eCRF page. Subjects are recorded as "Completed", "Screening failure", or "Early withdrawal". The date of the disposition event, date of last application of study drug and, if applicable, the date of death is recorded.

If applicable, the primary reason for discontinuation may include any of the following:

- Adverse Event (with a drop down to specify the AE number);
- Death;
- Inclusion not met/ Exclusion criteria met;
- Lack of efficacy;
- Lost to follow-up;
- Non-compliance with study drug;
- Occurrence of pregnancy;
- Physician's decision;
- Protocol violation;
- Withdrawal of consent;
- Withdrawal due to no pain;
- Other (with a free text to specify).

### 7.4.2 Demographic and Other Baseline Characteristics

Demographic data (Month and Year of Birth, Age, Sex, Race and Ethnicity) are recorded on the 'Demographics' eCRF page.

#### Age

Age (years) is manually entered into the eCRF.

#### Sex

Sex is recorded as "Male" or "Female".

#### Race

Race is recorded as "American Indian or Alaska Native", "Asian", "Native Hawaiian or Other Pacific Islander", "Black or African American", "White", "Unknown", "Not reported", or "Other (please specify)". More than one race may be selected.

#### Ethnicity

Race is recorded as "Hispanic or Latino", "Not Hispanic or Latino", "Not reported" or "Unknown".

## VAS

VAS score is recorded on the 'Visual Analogue Scale' eCRF page at screening and baseline.

Corrections to the scores are applied for scores recorded on or before 08JUL2024 due to the incorrect length of scale used in performing the test. This is documented in non-conformity number 61/2024. The following corrections are applied:

- For site **CCI** VAS score = raw VAS score x 0.82.
  - Correction factor calculated as:  $100 \div 122$  (actual length of scale)
- For site **CCI** VAS score = raw VAS score x 0.88.
  - Correction factor calculated as:  $100 \div 113$  (actual length of scale)

## 7.4.3 Medical/Surgical History and Concomitant Diseases

Relevant medical/surgical conditions, in the last year, including allergies or drug sensitivity, are recorded at the Screening visit on the 'Medical History' eCRF page.

The following variables are collected:

- Whether or not there are any medical/surgical conditions.
- For each condition: the event number (automatically prefilled), the reported term, the start date and, if applicable, the end date. If a condition is ongoing this is also recorded.

For each condition, not ongoing, the duration (days) is computed as:  $[(\text{Stop date} - \text{Start date}) + 1]$ .

Knee osteoarthritis diagnosis is recorded at the screening visit on the 'Knee Osteoarthritis Diagnosis' eCRF page.

The following variables are collected:

- Date of first diagnosis
- Whether the knee pain is affecting both knees (bilateral) or just one knee (unilateral)

Time since first diagnosis is computed as: Informed Consent Date - Date of First Diagnosis.

## 7.4.4 Prior and Concomitant Medication

Prior and Concomitant medication data are collected throughout the study on the 'Prior and Concomitant Medications' eCRF page. For each medication, the number (automatically prefilled), the trade or generic name is recorded with the following variables.

### Route

The route of administration is recorded as "Intraleisional", "Intramuscular", "Intraocular", "Intraperitoneal", "Intravenous", "Nasal", "Oral", "Rectal", "Respiratory (inhalation)", "Subcutaneous", "Topical", "Transdermal", "Vaginal", or "Other (please specify)".

### Dose

The dose of administration is recorded with the dose unit.

### Frequency

The frequency of administration is recorded as "Once", "Daily", "2 Times per day", "3 Times per day", "4 Times per day", "Every other day", "1 Time per week", "2 Times per week", "Every month", "As needed", "Unknown", or "Other (please specify)".

## Indication

The indication for the medication is recorded as “Adverse Event”, “Medical History”, “Procedure”, or “Other (please specify)”. If the indication is not “Other”, then the related Adverse Event, Medical History or Procedure is recorded.

## Start/End Date, Time, and Day

The start, end date and time is recorded. If the medication is ongoing this is recorded.

All medications have a start day and end day calculated as described in Section 7.2.

‘Prior medications’ are medications that were stopped before First Study Treatment Administration (end day < 1).

‘Concomitant medications’ are medications that were stopped on or after First Study Treatment Administration (end day  $\geq$  1 or are ongoing). These may have started at any time (i.e. prior to, on, or after, date of First Study Treatment Administration).

## 7.4.5 Concomitant Procedures

Concomitant procedures are recorded on the ‘Concomitant Procedures’ eCRF page. The procedure name, start date, end date (or ongoing), and indication (“Adverse Event”, “Medical History”, or “Other (please specify)”) is recorded. If the indication is “Adverse Event” or “Medical History” the related Adverse Event or Medical History is recorded.

## 7.4.6 Treatment Compliance and Exposure

### Total Number of Days on Study

Total Number of Days on Study is calculated as:

- Total Number of Days on Study = (Date of Study Completion / Discontinuation - Date of Screening Visit) +1.

### Total Number of Days in Treatment Phase

Total Number of Days in Treatment Phase is calculated as:

- Total Number of Days Treatment Phase = (Date of Study Completion / Discontinuation - Date of Baseline Visit)+1.

### Duration of Exposure

Duration of exposure is calculated as:

- Duration of exposure (days) = (Date of Last Study Treatment Administration - Date of First Study Treatment Administration) + 1

### Study Treatment Compliance

Study treatment compliance is determined from the ‘Study Product Use’ eDiary pages and calculated as:

- Treatment compliance (%) = (Number of days the answer to “Did you use yesterday the Voltaren Gel as per label and leaflet instructions?” is “Yes”  $\div$  Duration of exposure) \* 100.

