## **9 STUDY PROCEDURES**

This section lists the procedures to be completed at each planned study visit. The timing of each procedure is listed in the [Schedule of Activities](#) section.

Adherence to the study design requirements, including all procedures are essential and required for study conduct.

This section lists the procedures to be completed for each planned study time point. However, as per nature of RWE studies, if a subject fails to complete their daily questionnaires at any timepoint post-baseline, subjects will be permitted to continue in the study with missed dates recorded in the e-dairy.

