### **9.2.2 Days 1-21**

The number of days each subject will actively engage with the study will vary according to the baseline measurements. Voltaren Gel use will be limited to 21 days, but study

Property of Haleon - Confidential

May not be used, divulged, published or otherwise disclosed without the consent of  
 Haleon

Clinical Protocol Template, TMF-187821, v11.0. Parent SOP: [CCI](#)

subjects are allowed to stop using the product if they do not feel the need to continue using it (e.g., if the pain subsides). Study subjects will be told to use the products as per label instructions. Actigraph will collect mobility and sleep-related information continuously (24/7) throughout the study.

All questionnaires will be provided at pre-specified time-points during the study ([please see schedule of activities table](#)). Safety, adverse events, and use of concomitant medications will be monitored throughout the study. If a subject stops using the product before Day 21 (post baseline), they will be prompted to complete all relevant questionnaires before concluding the study.

The following assessments will be completed by subjects during the study period:

- Subjects will report any changes in health, concomitant medications, or non-drug treatments/procedures.
- Subjects will use Actigraph and complete additional QoL questions each day.
- Subjects will complete an eDiary to record product use each day.
- Subjects will report any adverse events.
- Subjects will report the end of product use and answer end of the study questions prior to exiting the study.

Subjects who do not use the product at all throughout the study will be considered as dropouts. Partial usage of the product across the treatment period (Day 7 to Day 21) is allowed to capture RWE usage of the product.

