## **12.3.6 Study Drug/Product Compliance and Use of Other Therapies**

### **13.3.6.1 Study Drug/Product Compliance**

Compliance and product use will be monitored throughout the study via eDiary and data transfers from Actigraph by relevant study personnel (Site Staff, CRO and Sponsor study team).

Study product compliance will be tabulated and summarized for the safety population. Summaries will include a simple yes/no frequency (and percent) count at each timepoint.

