### Date of First Study Treatment Administration

Date of first study treatment administration is derived as:

- (The earliest recorded date where the answer to the question “Did you use yesterday the Voltaren Gel as per label and leaflet instructions?” is “Yes” on the ‘Study Product Use’ eDiary page) - 1.

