### Date of Last Study Treatment Administration

Date of last study treatment administration is defined as:

- “Date of last application of study drug” as recorded in the ‘Study Termination’ eCRF page.).

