## 8. Analysis Methods

### 8.1 General Methods

Post-Text TLFs are provided in collated electronic PDF files.

For continuous variables, the mean, standard deviation, minimum, median and maximum are presented, together with the total number of observations and the number of missing and non-missing values. Unless otherwise specified, minimum and maximum values are reported to the same number of decimal places as the recorded measurements; mean and median are reported to one more decimal place and standard deviation one additional decimal place more than the mean.

For categorical variables, absolute and relative frequencies are reported. Relative frequencies are based on all observations and reported as percentages to one decimal place. Unless otherwise specified, percentages are based on the number of subjects with data and are not calculated for missing categories.

Adverse events are reported on a per-subject basis, i.e. if a subject reported several events coded to the same coding term the subject is counted only once at the respective level of display. The percentages are calculated using the number of subjects in the population Analysis Set as the denominator.

All hypotheses are tested at a 5% level of significance using a two-sided test unless otherwise specified.

P-values are rounded to three decimal places. If a p-value is less than 0.001 it is reported as "<0.001." If a p-value is greater than 0.999 it is reported as ">0.999.

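### SAP 7.4.6 counts an unanswered diary day between the first Yes and the eCRF last-application date as non-use of gel, so reported compliance mixes gel use with diary completion

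*SAP*

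**What the plan says.** SAP 7.4.6 defines the measure as "Treatment compliance (%) = (Number of days the answer to" the product-use question is Yes, divided by duration of exposure and multiplied by 100. The question asks whether the gel was used on the previous day.

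The denominator is a calendar span: "Duration of exposure (days) = (Date of Last Study Treatment Administration - Date of First Study Treatment Administration) + 1". Its two ends come from different sources (SAP 7.1):

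- The start is taken from the diary. It is "The earliest recorded date where the answer to the question" is Yes, minus one day.
- The end is taken from the Study Termination eCRF page, where it is recorded as "Date of last application of study drug".

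Neither section says what to do with a day that has no answer. SAP 8.2.5.1, written for endpoints, replaces no missing data except adverse event dates.

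The protocol expects missed diaries. Section 9 states that "if a subject fails to complete their daily questionnaires at any timepoint post-baseline, subjects will be permitted to continue in the study", and section 7.7 has missed assessments recorded as missed. For product compliance, protocol 13.3.6.1 says: "Summaries will include a simple yes/no frequency (and percent) count at each timepoint". On duration, protocol 9.2.2 states that "Voltaren Gel use will be limited to 21 days" and lets subjects stop earlier if they no longer need the gel.

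**The concern.** Gel use is known only for days on which the question was answered. Inside the exposure span, a blank day adds one to the denominator and nothing to the numerator, exactly as a No does. The protocol keeps No and missing apart, but the SAP percentage merges them. A subject who applies gel daily and skips some diary entries cannot then be distinguished from one who fills in every entry and skips some applications.

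Two smaller features of the same formula add to this. Use on the last day of a 21-day course cannot be reported, because the last scheduled diary is Day 21 and asks about Day 20. Also, Yes answers are not confined to the exposure span, so an eCRF last date earlier than the last diary-reported use can give more than 100%.

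At stake is how far a reader can trust the compliance row in a study whose purpose includes describing real-world use.

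**Working it through.** The documents state no compliance figure, target or threshold, so there is nothing to reproduce. The check applies the SAP formula to a defined subject.

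**Inputs**

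- Maximum course: 21 days (protocol 9.2.2). First use is taken as Day 1.
- Diary: one product-use entry per day about the day before. Entries on Days 2 to 21 cover Days 1 to 20, so d = 20 days can be answered.
- True use: every day (assumption, to isolate the effect of missed entries).
- Diary completion: c = 80% (assumption), so k = 0.80 × 20 = 16 answers, all Yes.
- E = true exposure in days: 20 if last use is Day 20, 21 if it is Day 21.
- L = unanswered days before the first Yes.

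**Formula.** The start date moves L days later, so reported compliance = 100 × k / (E − L).

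**No blank day before the first Yes (L = 0)**, so compliance = 100 × 20c / E:

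| Diary completion c | Last use Day 20 (E = 20) | Last use Day 21 (E = 21) |
|---|---|---|
| 100% | 20/20 = 100% | 20/21 = 95.2% |
| 90% | 18/20 = 90.0% | 18/21 = 85.7% |
| 80% | 16/20 = 80.0% | 16/21 = 76.2% |
| 70% | 14/20 = 70.0% | 14/21 = 66.7% |
| 60% | 12/20 = 60.0% | 12/21 = 57.1% |

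The gap between the two columns is caused by the previous-day wording, not by missed entries.

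**Blank days before the first Yes (c = 80%, k = 16)**

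| L | Chance if the 4 blanks fall at random | E = 20 | E = 21 |
|---|---|---|---|
| 0 | 0.800 | 80.0% | 76.2% |
| 1 | 0.168 | 84.2% | 80.0% |
| 2 | 0.028 | 88.9% | 84.2% |
| 3 | 0.003 | 94.1% | 88.9% |
| 4 | under 0.001 | 100% | 94.1% |

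The chances are C(19 − L, 15) / C(20, 16); for L = 0 this is 3876/4845 = 0.80. The mean is 81.0% for E = 20 and 77.1% for E = 21. So L = 0 is the usual case, but with the same completion and the same true use the score depends on when the entries were missed.

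**Non-use against non-reporting.** A subject with a full diary, 16 Yes and 4 No, whose first day is a Yes, also scores 16/20 or 16/21. The statistic gives the same value for both subjects.

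**Above 100%.** For illustration, take 20 Yes answers starting from Day 1 and an eCRF last date of Day 19: 20/19 = 105.3%.

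**Same subject with Yes/(Yes + No) inside the exposure window.** Compliance is 16/16 = 100% and diary completion is 16/20 = 80%, reported separately.

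**Why the window matters.** Take a subject who uses gel for 10 days, stops free of pain and answers No for the next 10. The SAP formula gives 10/10 = 100%. Yes/(Yes + No) over all answered days gives 10/20 = 50%. Limited to first through last administration, it gives 10/10 = 100%.

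**The case against.** Counting undocumented use as non-use is a recognised conservative choice. Protocol 7.7 bases adherence for withdrawn subjects on days active in the intervention, which is also a day-span denominator. The figure is descriptive: the SAP sets no cut-off on it, and neither the mITT definition (SAP 6.1), the MMRM (SAP 8.2.2) nor time to pain relief (SAP 7.4.7.3) uses it. SAP 10.1 tabulates eDiary visit attendance and SAP 10.5.1 lists all product-use data, so a determined reader can separate No from blank. A result above 100% needs two sources to disagree, which a data query could catch. All of this stands, and it limits the importance of the point. It does not supply a rule for blank days or label the percentage as a bound.

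A reader might infer more than the documents support:

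- *That every unanswered day is scored as non-use, so compliance simply equals diary completion.* It does not: blank days before the first Yes leave the denominator, and the score can then rise to 94.1% or 100%.
- *That the SAP contradicts its own general rule or the protocol.* SAP 8.1 says that "percentages are based on the number of subjects with data and are not calculated for missing categories", but that concerns categorical summaries across subjects and applies unless otherwise specified. The protocol's yes/no count is a cross-sectional summary at each timepoint. Both support the point only by analogy.
- *That 76 to 80% is what this trial will report.* The 80% completion rate is an assumption, and the lower end also requires use on Day 21, the day the product is returned.
- *That the usage correlations are biased.* SAP 8.2.4 does not name its usage measure.

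**Conclusion.** The point holds, and it is minor. Between the first Yes and the eCRF last-application date, each unanswered product-use day lowers reported compliance exactly as a reported non-use day would. For a daily user with no blank day before the first Yes, the shortfall equals the share of diary days missed: 20 percentage points at an assumed 80% completion (16/20). Last use on Day 21 lowers the score further, to 76.2%, and caps a complete diary at 95.2%. These figures rest on first use on Day 1, 20 answerable days and an assumed completion rate, since the plan gives none.

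The consequence is a descriptive safety-population percentage that cannot separate gel adherence from diary adherence. No efficacy conclusion depends on it. The exploratory correlations would be affected only if this percentage is the usage measure.

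**What to change.** In SAP 7.4.6:

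1. Assign each Yes or No answer to the day it refers to (diary date minus 1).
2. Count only days from first to last study treatment administration, in both numerator and denominator.
3. Define treatment compliance (%) as 100 × Yes days / (Yes days + No days) in that window.
4. Add a row for diary completion in the same window: answered days divided by days on which an answer was possible.
5. Keep the present ratio, with its numerator confined to the same window, labelled as the conservative bound that counts unanswered days as non-use.

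The window keeps permitted early stopping from being scored as non-compliance and makes values above 100% impossible. Any disagreement between the diary and the eCRF last date should still be queried.

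The cost is a SAP wording change and additional rows in the exposure table. The new percentage will look favourable if subjects skip the diary on the days they skip the gel, which is why all three figures are shown. The change does not recover blank days before the first Yes, because the start of exposure is itself taken from the diary; a footnote should say so.

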### Actigraph Device Compliance

The required Actigraph daily minimum wear time is 20 hours. Daily wear minutes is collected via the Actigraph device and converted to hours as:

- Daily wear time (hours) = Daily wear minutes ÷ 60.

Actigraph device compliance is calculated as:

- Actigraph device compliance (%) = (Number of days the daily wear time (hours) is greater than or equal to 20 hours ÷ Total number of days on study) \* 100

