## 1. Document History

Document Version	Date	Reason for changes
1.0	29OCT2024	Final version
2.0	05DEC2024	
Updates from the DRM:
 

• Section 7.1: Date of Last Study Treatment Administration updated include data collected in the End of Study Termination CRF

• Section 7.1: Study day definition updated to:

◦ Study Day = Date of assessment/event – Date of Baseline Visit.

• Section 7.1 Baseline derivation updated in line with new study day definition.

• Section 7.4.7 updated to exclude day 21 in the analysis due to Day 21 being a partial day.

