### 3.2 Study Design

This is a prospective, open-label, single-arm, multi-country (US and EU (Poland)) real-world evidence study assessing the effects of Voltaren Gel use on functional mobility and QoL in subjects with mild/non-serious osteoarthritis (OA) of the knee.

This study will utilise a research-grade validated wearable device: Actigraph, to objectively measure changes in functional mobility, alongside subjective assessments, providing the first subject-centric data on the real-world benefits of using Voltaren Gel, beyond pain relief.

The target population comprises male and female adults aged between 40 and 85 years, diagnosed with mild/non-serious osteoarthritis of the knee and self-reported pain at the time of recruitment.

This study adopts a hybrid approach, wherein participants are only obligated to be physically present for on-site screening (Day -7), end of baseline (Day 0), and end-of-study visits (Day 21). The remaining treatment phase (Day 1-21) will be conducted in a remote manner (e.g. at home) to observe the real-world usage of the product. The study period for each subject will last a maximum of 28 days.

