### **Awake Trigger Compliance**

Awake trigger compliance is determined from the 'Study Product Use' eDiary pages and calculated as:

- Awake trigger compliance (%) = (Number of days the answer to "Did you click the event trigger at awake yesterday?" is "Yes" ÷ Total Number of Days in Treatment Phase) \* 100.

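### The wear-compliance denominator counts the device dispensing and return days, so a fully compliant completer cannot score above about 92–93%

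*SAP*

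**What the plan says.** SAP 7.4.6 (Actigraph Device Compliance) requires 20 hours of wear per day. Compliance is the number of days with wear time "greater than or equal to 20 hours ÷ Total number of days on study", times 100. The denominator is defined in the same section: "Total Number of Days on Study = (Date of Study Completion / Discontinuation - Date of Screening Visit) +1".

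The site visits are "on-site screening (Day -7), end of baseline (Day 0), and end-of-study visits (Day 21"). The schedule of activities (Protocol Table 1-1, SAP Table 1) dispenses the tracker at the screening visit, after consent, and has it returned at Visit 3 on Day 21. The baseline period lasts 3 to 7 days (Protocol 9.2.1).

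Elsewhere the SAP treats the end days differently. Version 2.0 removed Day 21 from the tracker endpoints "due to Day 21 being a partial day" (SAP 1 and 7.4.7), and SAP 7.1 starts the tracker baseline at Day -6, which leaves out a Day -7 dispensing day.

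Awake and bedtime trigger compliance count the days answered Yes on the Study Product Use diary page to questions such as "Did you click the event trigger at awake yesterday". They divide by the Total Number of Days in Treatment Phase, which is completion date minus baseline visit date, plus 1.

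**The concern.** A compliance percentage should reach 100% for someone who did everything asked. This one cannot, because two days on which the criterion is out of reach always sit in the denominator. The SAP 2.0 change log lists edits to Sections 7.1 and 7.4.7 but none to 7.4.6, so a day dropped from the endpoint as partial still counts against the subject's compliance.

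What is at stake is how the compliance table is read. A reported 92–93% would look like 7–8% non-wear when it may reflect none. The shortfall also varies with time on study, so part of any difference between subjects would reflect baseline length or early completion and not behaviour.

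**Working it through.** The documents state no compliance percentage to reproduce, so this is a day count from the SAP formulas.

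**Can an end day reach 20 hours?** A calendar day allows 24 − 20 = 4 hours off the wrist. The device would have to be on by 04:00 on the screening day, and returned at or after 20:00 on Day 21. Visit clock times are not given, but on-site visits at such hours are implausible.

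**Wear ceiling.** Let b be the number of days from screening to the baseline visit and e the completion day.
- Denominator: e − (−b) + 1 = e + b + 1.
- Attainable days, strictly between the two end days: e + b − 1.
- Shortfall: 2 / (e + b + 1).

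| Baseline (days) | Completion | Attainable / counted | Ceiling |
|---|---|---|---|
| 7 | Day 21 | 27/29 | 93.1% |
| 6 | Day 21 | 26/28 | 92.9% |
| 5 | Day 21 | 25/27 | 92.6% |
| 4 | Day 21 | 24/26 | 92.3% |
| 3 | Day 21 | 23/25 | 92.0% |
| 7 | Day 14 | 20/22 | 90.9% |
| 7 | Day 7 | 13/15 | 86.7% |

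Early completion is foreseeable: Protocol 9.2.3 allows the study to end the day after last treatment if that falls before Day 21. If one of the two end days somehow reached 20 hours, the ceiling for completers would be 24/25 = 96.0% to 28/29 = 96.6%.

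**Trigger ceiling.** The denominator is 21 − 0 + 1 = 22 days. The numerator depends on when the diary page opens:
- Entries on Days 1–21 (the days on which the schedule marks product use): 21/22 = 95.5%.
- Entries on Days 2–21: 20/22 = 90.9%.
- Entries on Day 0 as well: 22/22 = 100%.

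The last case is unlikely. The same page asks whether the gel was used yesterday, and the gel is first dispensed on Day 0. But neither document gives the page dates.

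**Where the figures go.** SAP 10.5.1 puts exposure and compliance data in a summary table and a listing for the safety population. SAP 8.2 governs inclusion in the tracker analyses by counts: at least 3 valid days in baseline and in each post-baseline 7-day period, a valid day being at least 20 hours of wear. The percentage from 7.4.6 is not used there, in the mITT definition (SAP 6.1) or in the models (SAP 8.2.2).

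**The case against.** The strongest reply is that the SAP openly defines a denominator of all days on study. The result is conservative by a known two days, no stated figure is miscalculated, and a single-arm trial has no comparison to bias. Among subjects who complete to Day 21, the spread by baseline length is only 93.1 − 92.0 = 1.1 points. This stands as a limit on importance. It does not remove the mismatch, because the SAP sets Day 21 aside as partial in one section and counts it against the subject in another.

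A reader might infer that the reliability of the primary endpoint is in doubt because wear compliance is its main support. The documents do not support that: the SAP 8.2 rule controls data adequacy directly and does not use this percentage.

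A reader might also take 95.5% as an established ceiling for the triggers. It is not. The schedule marks product use on Days 1–21, which is not the same as stating when the diary page and its trigger items open. Protocol 6.5 asks for button presses during the study generally.

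Finally, it is tempting to reuse the Day -6 to Day 20 window as the wear denominator. That works only for a 7-day baseline. A fully compliant subject with a 3-day baseline would score 23/27 = 85.2%, worse than the present 92.0%.

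**Conclusion.** The wear part holds as a minor reporting defect. For subjects completing to Day 21, reported wear compliance is capped at 92.0% to 93.1%, with lower caps for early finishers. This rests on two assumptions: neither the dispensing day nor the return day reaches 20 hours, and the device is dispensed on the screening date and returned on the completion date. The SAP's treatment of Day 21, and of Day -7 on the full schedule, supports the first. With a baseline shorter than 7 days the dispensing day falls inside the Day -6 to Day 0 window, so for those subjects the assumption rests on the visit timing alone.

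The trigger part is probable but not established: 95.5% if entries run on Days 1–21, within a range of 90.9% to 100%.

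No efficacy estimate, test or analysis population changes.

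**What to change.** In SAP 7.4.6, define the wear denominator for each subject as the days from the day after device dispensing to the day before device return:

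- Wear denominator = return date − dispensing date − 1.

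Restrict the numerator to the same days. A fully compliant completer then scores 27/27 or 23/23 = 100%. Where dispensing and return coincide with screening and completion, this equals Total Number of Days on Study minus 2 (29 − 2 = 27; 25 − 2 = 23), so the dates already used are enough.

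For both trigger measures, use each subject's number of diary days on which the trigger question was due, and state in the SAP on which days the page opens. Do not fix this at 21, since subjects may finish early.

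The cost is two formula edits and the matching program changes, with no new data. If the present formulas are kept, the minimum is a table footnote giving the attainable maximum and noting that it falls with time on study.
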